Since 2006, the Hospital Sant Joan de Déu in Esplugues has successfully implemented OIT protocols for milk and egg in children over 5 years of age, accepting the associated risks. However, complete permanent desensitization has not been achieved in all patients. Many still experience occasional adverse reactions during maintenance. The success rate is estimated at around 70%, with failure mainly affecting children with anaphylaxis—those who would most benefit from protection.

2) OBJECTIVES

Main objective: To evaluate tolerance to baked foods in children under 6 years old who are allergic to cow's milk or egg proteins.

Secondary objectives:

- To evaluate tolerance to raw foods after one year of controlled intake of baked foods containing milk or egg in increasing amounts.
- To assess the immune response by identifying biomarkers that may predict the acquisition of tolerance.

- To compare quality-of-life questionnaires between patients tolerant to baked foods and their families versus those in the control group.
- To determine the individual reaction threshold dose that would allow patients to consume trace amounts of the allergen, thereby improving their quality of life and nutritional status.

3) METHODOLOGY

This is a prospective interventional study.

Inclusion criteria for cow's milk (CM):

- Children aged 12 months to 6 years with a clinical history suggestive of cow's milk protein allergy, and positive specific IgE and/or skin prick tests.

Inclusion criteria for egg:

- Children aged 12 months to 6 years with a clinical history suggestive of egg allergy, and positive specific IgE and/or skin prick tests.
- Children aged 12 months to 6 years sensitized to egg proteins (positive specific IgE and/or skin prick tests) without prior ingestion.

Exclusion criteria:

- Patients whose guardians do not sign the informed consent form (Annex 1).
- Patients with heart disease or conditions contraindicating the use of epinephrine.
- Patients who are already consuming baked products with milk or egg.

Complementary evaluations:

Skin prick tests, specific IgE, IgA, and IgG4 levels, regulatory T cells, IL-4, IL-5, IL-10, and TGF- β will be assessed at the beginning of treatment (T0) and after 12 months (T1). Basophil activation tests with cow's milk or egg proteins will also be performed before and after treatment.

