Eligible patients will undergo a baked food oral food challenge (OFC) at baseline. After 12 months of controlled intake, they will undergo another OFC with cooked and raw forms of the allergen.

Validated quality-of-life questionnaires for food allergy will be administered to families and children (depending on age) at baseline, during hospitalization for OFC, and at 12 months.

All OFCs will be performed at the hospital in a setting equipped to manage potential adverse reactions. Skin and blood tests will be performed 15 to 30 days before starting treatment.

BAKED FOOD CHALLENGE PROTOCOLS

Initial baked milk challenge:

Conducted using commercially available 6-cereal cookies (Almirón®), each containing 0.275 g of milk protein.

- Dose 1: 0.0375 g protein (1/8 cookie)
- Dose 2: 0.075 g protein (1/4 cookie)
- Dose 3: 0.15 g protein (1/2 cookie)
- Dose 4: 0.275 g protein (1 full cookie)
- Dose 5: 0.55 g protein (2 cookies)

Doses administered at 30-minute intervals. Vital signs are monitored before and after each dose. Observation continues for 3 hours post-final dose.

Initial baked egg challenge:

Conducted using Damira® cookies (free of cow's milk):

- Dose 1: ½ cookie (0.11 g protein)
- Dose 2: 1 cookie (0.22 g protein)
- Dose 3: 2 cookies (0.44 g protein)
- Dose 4: 5 cookies (1.1 g protein)

Doses administered at 30-minute intervals for the first two, then 60-minute intervals. Vital signs are monitored before and after. Observation continues for 3 hours post-final dose.

Cow's milk challenge:

Using pasteurized milk (3g/100mL) per PRACTALL protocol, followed by 125–200 mL final dose:

CM-OFC (ml)	CM-OFC (g)	Interval (minutes)
0.1	0.003	30
0.3	0.01	30
1	0.03	30
3	0.1	30
9	0.3	30
30	1	30
90	3	120
125/200	3.75/6	180 observation

Cooked egg challenge:

6-step protocol: 0.3, 1, 3, 9.5, and 30 g of hard-boiled egg white + 1 well-cooked omelet (7.5 g protein). Administered at 30-minute intervals (first 5 doses) and 120 minutes for final dose.

6-month dose escalation:

- Baked milk: 4 Almirón® cookies = 1.1 g milk protein.
- Baked egg: 1 homemade muffin (recipe in Annex 1) = 2 g egg protein. 3-hour observation post-dose.

4) STATISTICAL ANALYSIS

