All data will be analyzed using SPSS Version 26 (IBM Corp., USA) and/or GraphPad Prism Version 9 (GraphPad Software, Inc., La Jolla, Calif). Descriptive statistics will be performed for the total sample, as well as for the control and intervention groups. Results with p-values < 0.05 will be considered statistically significant.

Participants will be categorized as tolerant or non-tolerant based on their ability to tolerate 1 g of cow's milk protein or 2 g of egg protein. Student's t-test will be used to compare means of predictive variables. Differences in the distribution of clinical variables will be assessed using the Chi-square test or Fisher's exact test for categorical variables. For non-parametric data, the Mann-Whitney U test or Kruskal-Wallis test will be applied.

Receiver Operating Characteristic (ROC) curve analysis will be conducted to evaluate the diagnostic performance of each individual biomarker in predicting tolerance to baked

products. The accuracy of the test will be assessed using the area under the ROC curve (AUC), with an AUC > 0.7 considered acceptable. The performance of optimal cut-off points will be described in terms of sensitivity and specificity.

5) WORK PLAN AND TIMELINE

The principal investigator will be [name] [name]. Each study group will be led by a physician: Dr. [name] for egg-allergic patients and Dr. [name] for cow's milk protein-allergic patients. Data collection and processing will be handled by Dr. [name] and Dr. [name]. Laboratory determinations will be carried out by Dr. [name] (Hospital Clínic) and Dr. [name] (Hospital Sant Joan de Déu). All physicians and nurses in the department will be direct collaborators.

Patient recruitment will last 2 years. Approximately 80 patients will be included: 30 allergic to egg, 30 allergic to cow's milk protein, and 20 controls. Each patient will be followed for 12 months after randomization.

6) BUDGET

The principal investigator, responsible physicians, and collaborators will conduct the project within regular working hours without additional personnel costs. The main expenses are for laboratory studies, detailed below:

Study	Price per sample (€)
PBMC isolation	15
Antigen-specific proliferation assay	30
TH1/TH2/FOXP3 cytometry panel	60
BAT	99
Specific IgA determination	12
IgG4 determination	19

Estimated costs for 60 patients (T0)	Price 60 patients (euros)
PBMC isolation	900
Antigen-specific proliferation	1800
BAT	5940

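### In the cow's milk challenge, five of the eight gram labels are 11% above what the stated 3 g/100 mL gives, so reaction thresholds reported from that column would be overstated

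*Combined protocol and SAP*

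**What the plan says.** Section 3 (Cow's milk challenge) describes the test as "Using pasteurized milk (3g/100mL) per PRACTALL protocol". Its table has three columns: millilitres, grams and interval. The first seven steps are 0.1, 0.3, 1, 3, 9, 30 and 90 mL, labelled 0.003, 0.01, 0.03, 0.1, 0.3, 1 and 3 g. The closing row reads "125/200 3.75/6 180 observation", that is, 3.75 g for 125 mL or 6 g for 200 mL.

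This appears to be the raw-milk challenge given at the end of the study: "After 12 months of controlled intake, they will undergo another OFC with cooked and raw forms of the allergen".

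Two other places could draw on the gram figures. A secondary objective in section 2 is "To determine the individual reaction threshold dose", with a view to letting patients eat traces of the allergen. Section 4 sorts participants into tolerant and non-tolerant "based on their ability to tolerate 1 g of cow's milk protein or 2 g of egg protein". Section 4 does not say which challenge that refers to, or whether the amount is one dose or a running total.

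**The concern.** The stated concentration, the volume column and the gram column cannot all be right. Any two of them fix the third, and in five rows the third disagrees.

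What is at stake is a reported result. If thresholds are taken from the gram column, a child who reacts at one of those five steps is recorded as reacting to more protein than the stated milk contains. If they are computed from volume and concentration, the same child gets a lower figure. The plan does not say which to use, so two analysts could report different thresholds from the same challenge record.

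**Working it through.** **Inputs.** The concentration is 3 g/100 mL = 0.03 g/mL. Volumes and gram labels are those in the cow's milk challenge table (section 3).

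**Step 1: each row.** Grams = mL × 0.03. Implied concentration = label ÷ mL × 100.

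| mL | Label (g) | Computed (g) | Label ÷ computed | Implied g/100 mL |
|---|---|---|---|---|
| 0.1 | 0.003 | 0.003 | 1.00 | 3.00 |
| 0.3 | 0.01 | 0.009 | 1.11 | 3.33 |
| 1 | 0.03 | 0.03 | 1.00 | 3.00 |
| 3 | 0.1 | 0.09 | 1.11 | 3.33 |
| 9 | 0.3 | 0.27 | 1.11 | 3.33 |
| 30 | 1 | 0.9 | 1.11 | 3.33 |
| 90 | 3 | 2.7 | 1.11 | 3.33 |
| 125 | 3.75 | 3.75 | 1.00 | 3.00 |
| 200 | 6 | 6.00 | 1.00 | 3.00 |

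The plan's figures are reproduced at 0.1, 1, 125 and 200 mL, and not at the other five volumes.

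**Step 2: does rounding explain it?** Rounding the computed values to one significant figure accounts for 9 mL (0.27 to 0.3) and 90 mL (2.7 to 3). It leaves 0.009, 0.09 and 0.9 unchanged, so it does not account for 0.3, 3 or 30 mL. Rounding to one decimal place leaves 0.9 and 2.7 unchanged.

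Starting instead from 3.33 g/100 mL, one significant figure reproduces all seven steps up to 90 mL (0.1 mL gives 0.00333, printed 0.003; 1 mL gives 0.0333, printed 0.03). The closing row then fails: 125 × 0.0333 = 4.17 g and 200 × 0.0333 = 6.67 g, against 3.75 and 6 g. No single concentration fits the whole table.

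**Step 3: cumulative dose.**
- Through 9 mL: 13.4 mL × 0.03 = 0.402 g; labels add to 0.443 g.
- Through 30 mL: 43.4 mL × 0.03 = 1.302 g; labels add to 1.443 g.
- Through 90 mL: 133.4 mL × 0.03 = 4.002 g; labels add to 4.443 g (ratio 1.11).

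**Step 4: size relative to the dose steps.** Up to 90 mL, each volume is 3 or 3.33 times the one before, so the challenge locates a threshold only within about a threefold interval. The label error is a factor of 1.11. The last step is narrower: from 90 to 125 mL the volume rises by 39% (125/90 = 1.39), while the labels rise by 25% (3.75/3 = 1.25).

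**Step 5: the 1 g cut-off.** At 3 g/100 mL, 1 g is 1/0.03 = 33.3 mL, so the single 30 mL dose is 1 g by label and 0.9 g by computation. On a cumulative basis, 1 g is not reached at 9 mL (0.402 or 0.443 g) and is passed at 30 mL (1.302 or 1.443 g) under either set of figures.

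The baked-food figures in section 3 lie close to the same cut-off. The initial baked milk doses, as printed, add to 0.0375 + 0.075 + 0.15 + 0.275 + 0.55 = 1.0875 g. The six-month baked milk dose is 4 × 0.275 = 1.1 g. The six-month baked egg muffin is given as 2 g, exactly the egg cut-off.

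**The case against.** The strongest reply is that the labels are nominal. The first seven form a regular series, alternating 3s and 1s across powers of ten, paired with volumes that are easy to measure; the closing dose was added and calculated separately. The concentration is given to one significant figure, so 0.9 g is no firmer than 1 g as a statement about the milk in the cup. If 3 is read as anything from 2.5 to 3.5 g/100 mL (an assumption), 30 mL holds 0.75 to 1.05 g. The volumes are printed beside the grams, so nothing is lost, and 11% is minor beside threefold steps.

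Most of this stands. It explains how the mismatch probably arose and keeps it small. It does not remove the mismatch: the protocol never calls the labels nominal, and it gives no rule for which figure enters a reported threshold.

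A reader might infer two stronger things. The first is that children who tolerate 30 mL and react at 90 mL will be misclassified, because the 30 mL label falls on the 1 g cut-off. That requires the cut-off to refer to this challenge and to a single dose. Section 4 says neither. The baked-food figures point elsewhere, as does the ROC analysis in section 4, whose target is tolerance of baked products. This challenge also continues well past 1 g.

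The second is that overstated thresholds would make trace intake unsafe. The objective links thresholds to trace intake, but no rule in the documents converts this gram column into a permitted amount, so that harm is not shown.

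**Conclusion.** The inconsistency is real and certain as arithmetic: five of the eight rows are labelled 11% above the stated concentration, and three match it exactly. The consequence that follows from the documents is limited to thresholds reported in grams. These would be overstated by 11% at the 0.3, 3, 9, 30 and 90 mL steps, and by 0.44 g in 4.00 g cumulatively through 90 mL. This assumes that the stated 3 g/100 mL describes the milk used and that thresholds are taken from the gram column.

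An effect on tolerance classification is conditional on an unstated reading of section 4 and should not be claimed. This is a small correction, worth making because it affects a figure the trial sets out to report.

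**What to change.** 1. In section 3, reconcile the concentration, volume and gram columns of the cow's milk challenge. If the gram labels are meant as nominal step names, say so.
2. Record the volume each child takes at each step, and derive the reported threshold as that volume times the concentration of the milk used. State whether it is a single-step or a cumulative amount.
3. Have the sponsor reconcile section 4 with the challenge tables by stating which challenge the 1 g cut-off refers to, and whether it is a single or a cumulative dose. Which value governs tolerance is for the sponsor to decide; this point takes no position on it.

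The cost is one corrected table, one derivation rule and one clarifying sentence. None of this requires a change to the volumes given. The downside is that some reported thresholds become about 10% lower (for example 0.9 g in place of 1 g).

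### Sensitivity and specificity at data-chosen optimal cut-offs will be too favourable on average, and AUC > 0.7 is a point-estimate grade with no interval

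*Combined protocol and SAP*

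**What the plan says.** Identifying predictive biomarkers is a secondary objective in section 2: "To assess the immune response by identifying biomarkers that may predict the acquisition of tolerance".

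Section 4 sorts children into tolerant and non-tolerant "based on their ability to tolerate 1 g of cow's milk protein or 2 g of egg protein". It then plans ROC analysis to "evaluate the diagnostic performance of each individual biomarker in predicting tolerance to baked" products. Accuracy is judged by the AUC, "with an AUC > 0.7 considered acceptable". For the cut-offs the plan says: "The performance of optimal cut-off points will be described in terms of sensitivity and specificity".

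No section states how an optimal cut-off is found, names one in advance, gives an interval for AUC, sensitivity or specificity, or provides for cross-validation, resampling or a second sample. Nor does the plan say whether ROC curves are run per allergen or pooled.

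Section 3 (complementary evaluations) lists ten candidate markers: skin prick test, specific IgE, IgA, IgG4, regulatory T cells, IL-4, IL-5, IL-10, TGF-β and the basophil activation test. Section 6 also costs a proliferation assay. The cytokines, the cytometry panel and IgG4 wait for other grants; they are deferred, not dropped.

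**The concern.** With no pre-set value and no validation sample, the natural reading of an optimal cut-off is one picked from the study data. A cut-off that maximises apparent performance in about 30 children partly fits chance. Sensitivity and specificity read off in those same children carry that chance with them, in the favourable direction. This happens for a single marker, useful or useless, and needs no assumption about how many are tested.

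The AUC grade raises a different problem. It is applied to an observed value without an interval, so in small groups an uninformative marker can be called acceptable, and the chance grows with the number of markers examined.

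At stake is how far a reader can trust a published cut-off and its accuracy for predicting tolerance to baked milk or egg.

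**Working it through.** **Inputs from the documents.** Section 5: 30 egg-allergic + 30 milk-allergic + 20 controls = 80, which adds up. There is no power, precision or expected tolerance figure to reproduce. Four of the ten markers (skin test, specific IgE, IgA, basophil test) are not said to await other grants.

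**Assumptions.** Tolerant share 50-80%, so splits from 15/15 to 24/6 at n=30 and from 30/30 to 48/12 if the foods are pooled at n=60. Cut-off at the maximum Youden index J = sensitivity + specificity − 1. Marker normal with equal variance in both groups, direction fixed in advance. The 20 controls do not enter.

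**Step 1: cut-off optimism.** For true AUC A, the group means differ by δ = √2·Φ⁻¹(A). The apparent J is the largest J in the sample. The true J at the chosen cut-off c is Φ(δ−c) + Φ(c) − 1. At A = 0.80 the best J attainable at any cut-off is 0.448; at A = 0.50 it is 0. Means over 20,000 simulated data sets per setting:

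| Split | Apparent J, A=0.80 | True J at that cut-off | Apparent J, A=0.50 (true 0) |
|---|---|---|---|
| 15/15 | 0.773+0.793−1 = 0.566 | 0.676+0.734−1 = 0.410 | 0.197 |
| 21/9 | 0.767+0.815−1 = 0.582 | 0.698+0.711−1 = 0.409 | 0.218 |
| 24/6 | 0.760+0.844−1 = 0.604 | 0.703+0.701−1 = 0.404 | 0.247 |
| 30/30 | 0.755+0.775−1 = 0.530 | 0.692+0.730−1 = 0.422 | 0.146 |
| 48/12 | 0.748+0.808−1 = 0.556 | 0.711+0.705−1 = 0.416 | 0.184 |

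Separate runs put the n=30 apparent values at 0.56-0.61 (A=0.80) and 0.20-0.25 (A=0.50).

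**Step 2: is the AUC itself biased?** For one pre-specified marker, no: with true AUC 0.70 the mean observed AUC was 0.700. If only markers observed above 0.7 are kept, the mean among them is 0.77-0.79 at n=30 and 0.75-0.77 at n=60.

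**Step 3: how often does an uninformative marker pass?** AUC = U/(n₁n₂), so the exact Mann-Whitney null distribution gives p = P(AUC > 0.7). For four independent markers the chance of at least one pass is 1 − (1−p)⁴.

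| Split | p | At least one of four |
|---|---|---|
| 15/15 | 0.0306 | 1 − 0.9694⁴ = 12% |
| 21/9 | 0.0428 | 1 − 0.9572⁴ = 16% |
| 24/6 | 0.0713 | 1 − 0.9287⁴ = 26% |
| 30/30 | 0.0035 | 1 − 0.9965⁴ = 1% |
| 48/12 | 0.0158 | 1 − 0.9842⁴ = 6% |

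At correlation 0.5 between markers, the n=30 range falls to about 10-20%. If each marker's direction is chosen from the data, it rises to 22-46% (independent markers). It also falls if some of the four are truly informative.

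**Step 4: what an interval would show.** At an observed AUC of 0.70 the Hanley-McNeil 95% interval is 0.51-0.89 (15/15), 0.50-0.90 (21/9) or 0.48-0.92 (24/6); at n=60 it is 0.57-0.83 to 0.55-0.85. A specificity of 7/9 has an exact 95% interval of 0.40-0.97, even with the cut-off treated as fixed.

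**Step 5: which correction works?** At n=30, each method repeating the cut-off search:

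| | True J | Bootstrap optimism correction | Repeated stratified cross-validation |
|---|---|---|---|
| Uninformative marker | 0 | 0.09-0.11 | −0.01 to 0.01 |
| True AUC 0.80 | 0.40-0.41 | 0.46-0.50 | 0.39-0.41 |

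Cross-validation removes the bias over all markers; the bootstrap removes only part of it. Neither undoes selection: among uninformative markers that pass AUC > 0.7, the cross-validated index is still about 0.33.

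**The case against.** The plan's own measure of accuracy is the AUC, and that is unbiased for a single pre-specified marker. This stands. A reader might infer that biomarker accuracy as a whole will be overstated; the documents do not support that. The expected bias is in sensitivity and specificity at the chosen cut-off. The AUC is inflated only among markers singled out for passing, or when direction is taken from the data.

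A reader might also infer that the AUC grade conflicts with the planned tests, since "Results with p-values < 0.05 will be considered statistically significant", the "t-test will be used to compare means of predictive variables" and, for non-parametric data, "the Mann-Whitney U test or Kruskal-Wallis test will be applied". The conflict is minor and changes sign. At 15/15 the smallest passing AUC is 158/225 = 0.702 and Mann-Whitney significance needs 0.716; at 24/6 it needs 0.77. Pooled at n=60, significance needs only 0.65-0.69, so the AUC grade is the stricter rule. No decision is attached to the grade, so it need not match a test.

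The sizes depend on who is analysed. Section 5 mentions randomisation but does not say whether controls enter the ROC analysis. If they added ten per food (n=40), the one-marker false-pass rate would be 1.4-4.1%. The budget is for 60 patients, which favours excluding them for the costed assays but does not settle it for skin tests and specific IgE.

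Finally, the objective speaks of markers that may predict tolerance. For a secondary aim of that kind, formal multiplicity adjustment and mandatory per-allergen curves are matters of choice. That also stands, though it does not excuse biased sensitivity and specificity.

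**Conclusion.** The point holds for sensitivity and specificity. Followed as written, section 4 gives figures that are too favourable on average: at n=30 the Youden index is overstated by about 0.16-0.20 for a marker with true AUC 0.80 and by 0.20-0.25 for an uninformative one. At n=60 the corresponding figures are about 0.11-0.14 and 0.15-0.18. These sizes rest on the Youden criterion, the assumed tolerant share, the normal model for the informative marker and the exclusion of controls. The direction of the bias needs only that the cut-off is chosen to do well in the children in whom it is scored, which is an inference from the plan's silence but the natural one.

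The AUC grade is a lesser matter: without an interval, it passes a single uninformative marker in 3-7% of samples at n=30 and in about 0.3-1.6% at n=60.

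Neither the main objective nor any treatment allocation depends on this analysis. It is a cheap improvement, confined to the secondary biomarker conclusions.

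**What to change.** In section 4:

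1. Fix each marker's direction and the cut-off criterion (for example Youden) before analysis.
2. For every marker tested, report sensitivity and specificity from repeated stratified cross-validation that repeats the cut-off search in each training set, beside the apparent values.
3. Give 95% confidence intervals for AUC, sensitivity and specificity.
4. Treat AUC > 0.7 as a descriptive grade, state how many markers were tested, and call the cut-offs exploratory until validated in other patients.

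State also whether curves are per allergen or pooled and whether controls enter. Multiplicity-adjusted p-values are optional.

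The cost is a few sentences and a short script, possibly outside the two named packages. The reported figures will be less favourable and more variable. Selection bias remains among markers singled out for passing AUC > 0.7, which is why results should be shown for every marker.

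### Follow-up is counted from a randomisation the plan never describes, controls have no dated start, and the one stated control comparison takes a group by challenge result with only unadjusted tests on offer

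*Combined protocol and SAP*

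**What the plan says.** All references are to the combined protocol and SAP.

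- **Section 5 (Work plan and timeline)** gives the groups: "Approximately 80 patients will be included: 30 allergic to egg, 30 allergic to cow's milk protein, and 20 controls". The next sentence sets the follow-up: "Each patient will be followed for 12 months after randomization". This is the only mention of randomisation.
- **Section 3 (Methodology)** labels the design: "This is a prospective interventional study". It describes the path of the children: "Eligible patients will undergo a baked food oral food challenge (OFC) at baseline". For the end of the study it says: "After 12 months of controlled intake, they will undergo another OFC with cooked and raw forms of the allergen". Laboratory measures "will be assessed at the beginning of treatment (T0) and after 12 months (T1"). Questionnaires are due at baseline, during the hospital stay for the challenge, and at 12 months.
- **Section 2 (Objectives)** contains the one explicit comparison with controls: "To compare quality-of-life questionnaires between patients tolerant to baked foods and their families versus those in the control group".
- **Section 4 (Statistical analysis)** says: "Descriptive statistics will be performed for the total sample, as well as for the control and intervention groups". It classifies participants as tolerant or not by the amount of protein tolerated. The tests it lists are the t-test, chi-square or Fisher's exact test, Mann-Whitney and Kruskal-Wallis. No covariate adjustment is mentioned.

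The plan gives no sequence, ratio, concealment, strata or allocation visit. It gives the controls no eligibility criteria, source, allergen or management of their own.

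**The concern.** Two things cannot be settled from the text.

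First, a reader cannot tell whether a difference between treated children and controls is protected by random allocation. If it is not, the groups may differ in age, food, severity or family choice, and an unadjusted p-value mixes those differences with any effect of the diet.

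Second, the 12 months have more than one stated origin. Treated children have a usable one. Controls have no described treatment or controlled intake, so the only origin that could date their follow-up is the undescribed randomisation. If some children outgrow milk or egg allergy with age, groups measured on different clocks could differ for that reason alone.

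The quality-of-life comparison is the most exposed. Its treated side is restricted to children who tolerate baked food. Passing a challenge may itself go with milder allergy and better quality of life, so the comparison can be distorted whatever happens at allocation.

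**Working it through.** **1. Group sizes.** 30 + 30 + 20 = 80, which reproduces the stated total. The overall 60:20 split is no evidence either way, because 3:1 randomisation would give the same numbers.

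**2. Time origins side by side.**

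| Place | 12 months counted from | Covers controls? |
|---|---|---|
| Section 5, follow-up | randomisation | only if controls are randomised; no procedure given |
| Section 3, laboratory tests | beginning of treatment (T0) | no treatment described for controls |
| Section 3, final challenge | controlled intake | no intake described for controls |
| Section 3, questionnaires | baseline | not restricted to treated children, but baseline is undated for controls |

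Treated children have a consistent T0, which needs reconciling with Section 5. Controls have no dated start.

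**3. The control comparison.** Section 3 goes from eligibility to the baseline baked-food challenge and then to controlled intake, with no allocation step between. Section 2 then takes the tolerant children and sets them against controls. On that path, one group is formed after a result is known and the other by an unstated route.

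**4. Size, under assumptions.** The documents give no imbalance, no outcome SD and no number tolerant. Suppose there is no true effect, but an uncorrected difference of δ (in SD units) reaches the outcome mean. For a two-sample t-test at two-sided 0.05 (Section 4 gives 0.05; two-sided is assumed):

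- SE = √(1/n₁ + 1/n₂)
- non-centrality = δ / SE
- false-positive rate = P(|T| > critical value), with T non-central t on n₁ + n₂ − 2 degrees of freedom

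With 60 v 20, SE = √(1/60 + 1/20) = 0.258 on 78 df. With 30 v 20, where 30 tolerant is an assumption, SE = √(1/30 + 1/20) = 0.289 on 48 df.

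| δ (SD, assumed) | 60 v 20: δ/SE | Rate | 30 v 20: δ/SE | Rate |
|---|---|---|---|---|
| 0.2 | 0.775 | 11.9% | 0.693 | 10.4% |
| 0.3 | 1.162 | 20.9% | 1.039 | 17.5% |
| 0.5 | 1.936 | 48.1% | 1.732 | 39.7% |

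Here δ is a shift in the outcome. A baseline imbalance carries over only in part: at an assumed baseline-outcome correlation of 0.5, an imbalance of 0.5 SD becomes δ = 0.5 × 0.5 = 0.25. The same formula then gives 16.0% with 60 v 20 and 13.6% with 30 v 20.

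**The case against.** The strongest reply is that this is one loosely used word in a timeline. The main objective needs no control group, and no objective or analysis is called randomised or causal. Treated children have T0 and 12 months of controlled intake. The questionnaires, on which the only explicit control comparison rests, have their own baseline and 12-month schedule. Section 4 promises only descriptive statistics for control and intervention groups. It ties the t-test to predictive variables, in the paragraph that splits participants by tolerance, and does not assign chi-square to the control comparison.

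Much of that stands, and it rules out three stronger readings that a reader might infer:

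- **That no child is randomised.** The documents never say so. Section 5 implies allocation, and the Section 3 label fits either design. The supportable statement is that no procedure is described.
- **That the 12-month clock has no valid start.** This is wrong for treated children. The gap concerns controls.
- **That a tolerant-versus-control comparison could never be randomised.** It could, if children who pass the baseline challenge were then allocated to intake or control. The plan does not describe that order.

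The false-positive figures also rest on assumed shifts and cannot be read as this trial's error rate.

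The reply does not remove the need to act. Section 2 does plan a comparison with controls, Section 4 offers nothing but unadjusted tests for it, and baseline remains undated for the controls.

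**Conclusion.** The point holds as a problem of inconsistency and interpretation. Section 5 relies on a randomisation that the plan nowhere describes. The stated time origins differ, and none dates the start for controls. The quality-of-life comparison selects one side by challenge result and has no planned adjustment, so as described it cannot be read as a protected randomised comparison.

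The consequence could be material. A modest uncorrected shift of 0.2 SD would roughly double the nominal 5% error, and 0.5 SD would take it to 40% or more. Those figures assume that the shift reaches the outcome in full, that the groups are 60 v 20 or 30 v 20, and that a two-sided t-test is used. The true imbalance and the number tolerant are unknown.

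The change should be made, but the evaluation of tolerance to baked food under the main objective does not depend on it.

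**What to change.** 1. **State whether children are randomised.**
   - If they are, describe the method and ratio, say when allocation occurs relative to the baseline challenge, and compare children as allocated.
   - If they are not, delete the reference to randomisation in Section 5, say how controls are chosen, and call control comparisons non-randomised.
2. **In either case, define one index date for each group** and use it in Sections 3 and 5: start of controlled intake for treated children, the baseline visit for controls. Section 3 places skin and blood tests 15 to 30 days before treatment, so the text should also say which contact counts as the controls' baseline visit.
3. **In Section 4, name the analysis of the control comparison:** the 12-month quality-of-life difference, adjusted for baseline score and age. Add food only if controls have milk or egg allergy, which the plan does not state.
4. **Describe the result as an association** wherever groups are formed by challenge result or are not randomised.

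The cost is wording in Sections 3 to 5 and one regression model. Baseline and 12-month questionnaires are already scheduled, but the plan should confirm that controls complete both. The downsides are slightly more analysis and, if there is no randomisation, a weaker design label.
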